Off-label use for adults with newly diagnosed ITP has been described in two small single-center trials. A single-arm study of dexamethasone in combination with 4 weeks of eltrombopag used upfront in adult patients with newly diagnosed ITP produced 100% response (platelets $>30 \times 10^9/L$) at completion of therapy, and 66.7% relapse-free survival at 1 year, better outcomes than expected for comparable patients treated with steroids alone.⁸ In a second study, 76% of steroid-nonresponsive patients had a durable response to eltrombopag after 3 months of therapy.⁹ Based on data from ICON2, pediatric hematologists are already using TPO-RAs in some cases of newly diagnosed ITP. Of 79 patients described in the ICON2 retrospective review who were prescribed a TPO-RA, 18% had newly diagnosed ITP.¹⁰ TPO-RAs may be an efficacious first-line therapy for newly diagnosed ITP patients who require treatment.

While age and duration of symptoms at diagnosis are known to predict resolution of ITP¹¹, other biologic factors that predispose some patients to resolution of their ITP and others to a more chronic course are not known. It is also not known whether the development of chronic ITP could be prevented by intervention earlier in the patient's course. A subset of patients with chronic ITP has been reported to have resolution of their disease after treatment with TPO-RAs, which was sustained after discontinuation of the medication. One postulated mechanism is immune tolerance by increasing exposure to platelet antigens, a hypothesis supported by the decreasing titer of anti-platelet antibody in one patient who resolved.¹² Another proposed mechanism is the increase in Treg functionality due to increased TGF- β 1 released by megakaryocytes.¹³ Because of the implication of Tregs in the pathogenesis of ITP and the potential immunomodulatory effects of TPO-RA, early use of eltrombopag may have an impact on the number of patients who resolve versus have persistent or chronic disease. Additionally, there are likely other biological factors which influence response to TPO-RA and other therapies that are not yet understood. Identification of these biomarkers could lead to a more personalized approach to therapy, targeted to an individual patient's disease biology.

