4 STUDY DESIGN

This is a prospective, open label, randomized, two-arm, multi-center Phase 3 trial. Patients with newly diagnosed ITP are randomized 2:1 to receive the experimental treatment, eltrombopag, or investigator's choice of 3 standard therapies. The primary objective is to determine if the proportion of patients with platelet response is significantly greater in patients treated with eltrombopag compared to those treated with standard therapies.

Randomization at study enrollment will be stratified by the two factors described below, using a block size of 3.

- a) Age at enrollment
- b) Whether the patient has received a first-line treatment (as defined in inclusion criteria):
 - **1) Upfront treatment:** Patients *within 10 days* of ITP diagnosis who have not received previous treatment
OR
 - **2) Treatment failure:** Patients who have failed standard management (observation or treatment with one or more first-line standard agents)

Table 4A: Stratification strata and stratum-specific patient enrollment limits

Stratum	Patient Age at Enrollment	Patient Up-front Treatment Status	Maximum Number of Patients Enrolled
1	1 – <6	Requires up-front treatment	27
2	1 – <6	Failed up-front treatment	27
3	6 – <12	Requires up-front treatment	27
4	6 – <12	Failed up-front treatment	27
5	12 – <18	Requires up-front treatment	27
6	12 – <18	Failed up-front treatment	27

Patients randomized to the eltrombopag arm will be eligible to continue the treatment throughout the 1-year duration of study participation, with guidelines given for dose adjustments.

A total of up to 162 patients will be enrolled. The required sample size is 147 “informative” patients (as defined below), with 104 (estimated 98 informative) in the experimental treatment arm and 52 (estimated 49 informative) in the standard treatment arm. A conservatively high estimate of 9% of patients are anticipated to withdraw from the study prior to the 5-week platelet assessment; these patients will be classified as non-responders, and will make a non-informative contribution to the analysis response rate for the primary objective. Therefore, to obtain at least 147 informative randomized patients, we plan to enroll and randomize up to an additional 15 patients (9 and 6 for the eltrombopag and standard treatment arms, respectively) for a total of 162.

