5.3 Exploratory Endpoints

5.3.1 Platelet-specific endpoints

- Time to response (platelets $>30 \times 10^9/L$, and at least 2-fold increase in the baseline count and absence of bleeding) (IWG definition)¹⁷
- Treatment response (platelets $>30 \times 10^9/L$, and at least 2-fold increase in the baseline count and absence of bleeding) (IWG definition) at 12 weeks
- Time to platelet count $>100 \times 10^9/L$ and absence of bleeding (IWG definition)
- Treatment response (platelet count $>100 \times 10^9/L$ and absence of bleeding) (IWG definition) at 12 weeks
- Loss of treatment response (platelet count below $30 \times 10^9/L$, or less than 2-fold increase in the baseline count or bleeding) (IWG definition) at any time during the study period after achieving response during the first 12 weeks
- Extreme thrombocytosis (platelets $>1 \times 10^{12}/L$)

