16 STATISTICAL METHODS AND CONSIDERATIONS

Overview

This is a prospective, open label, randomized, two-arm, multi-center Phase 3 trial. Enrolled patients with newly diagnosed ITP are randomized at enrollment 2:1 to the experimental treatment arm (eltrombopag) and standard treatment arm (investigator's choice of 3 standard therapies); randomization will be stratified by patient's age at enrollment and up-front treatment status, with block size of 3. Each stratum will be limited to a maximum of 27 patients. Hence, the age distribution of the final accrued cohort may not be representative of the patient population. This is appropriate in the context of this study to ensure sufficient number of patients to study treatment effects in each age group. The primary objective is to determine

whether the proportion of patients with platelet response is greater in the experimental treatment arm compared to the standard therapy arm using a one-sided Cochran-Mantel-Haenszel (CMH) test at alpha=0.025 (see section 16.b).

Intent-to-Treat and Evaluability

For the primary objective, all randomized patients will be included in an intent-to-treat (ITT) analysis. Evaluability for the secondary and exploratory objectives: In the experimental treatment arm, patients will be considered evaluable if they receive at least one dose of eltrombopag. In the standard treatment arm, patients will be considered evaluable if they receive at least one dose of one of the standard of care treatments.

Statistical Analysis

a. Baseline Demographic and Clinical Characteristics

Patient demographic and clinical characteristics at study enrollment will be summarized using descriptive statistics, including frequencies and proportions for categorical measures, and means, medians, ranges, and standard errors for continuous measures.

b. Analysis of Primary Endpoint

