To address secondary objective 3.2.11, the frequency and proportion (with 95% confidence interval) of patients with abnormal LFTs will be calculated. Adverse event rates will be coded by body system and MedDra classification term. Adverse events and serious adverse events will be tabulated by treatment group and will include the number of patients for whom the event occurred, the rate of occurrence, and the severity and relationship to study drug. If a patient experiences the same toxicity multiple times, a patient will be counted only once for a given toxicity at the maximum grade.

d. Analysis of Exploratory Objectives

Exploratory objectives are hypothesis-generating only. Any exploratory findings need to be confirmed in an independent study.

To address the platelet exploratory objectives 3.3.1, a Cochran-Mantel-Haenszel test will be used to compare the proportion of patients between treatment arms with: (1) specific platelet-defined treatment response at 12 weeks, (2) extreme thrombocytosis, and (3) loss of treatment response (in the subgroup of patients who achieved treatment response during the first 12 weeks. Cumulative incidence curves by treatment arm will be created to describe: (1) time to response and (2) time to platelet and bleeding response. Gray's test will be used to compare the cumulative incidence between treatment arms.

To address the patient-reported outcomes exploratory objectives 3.3.2, KIT scores and fatigue scores will be calculated as described. Spaghetti plots will be used to visualize the scores over time per patient by treatment arm. An ANCOVA model will be used to compare the absolute change from baseline at 1 week, 4 weeks, 12 weeks, and 1 year between the two arms.

To analyze the non-survey endpoints of exploratory objective 3.3.3, a Cochran-Mantel-Haenszel test (for categorical outcomes) or an ANCOVA model (for

continuous outcomes, like the cost of therapy) will be used to compare the two arms.

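### The exploratory Gray's test for time to response names no strata although randomisation is stratified; if the strata are prognostic, an unstratified test is conservative

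*Combined protocol and SAP*

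**What the plan says.** Section 4 fixes the design: "Randomization at study enrollment will be stratified by the two factors described below, using a block size of 3". The overview of section 16 repeats the factors, "age at enrollment and up-front treatment status, with block size of 3". Three age bands and two treatment-status levels make six strata, and "Each stratum will be limited to a maximum of 27 patients".

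Section 16.d covers exploratory objective 3.3.1. The binary platelet endpoints get a Cochran-Mantel-Haenszel (CMH) test. The two time-to-event endpoints of section 5.3.1 (the IWG response, and platelets above 100 × 10⁹/L without bleeding) get cumulative incidence curves by arm, and Gray's "test will be used to compare the cumulative incidence between treatment arms". The text does not say whether that test is stratified, and it gives the test no significance level, sidedness or power.

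Two other statements bear on the point. Section 16.d opens with "Exploratory objectives are hypothesis-generating only" and "Any exploratory findings need to be confirmed in an independent study". The Background says "While age and duration of symptoms at diagnosis are known to predict resolution of ITP", but no section gives the size of either stratification factor's effect on time to response.

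**The concern.** Blocking within strata forces the arms to be balanced on the stratification factors, so differences between strata add almost nothing to the chance variation of the treatment comparison. An unstratified test does not know this. Its variance is computed as if the whole cohort had been allocated freely, so it still includes the between-stratum spread. If the strata differ in speed of response, the variance is too large, the p-value is too large on average, and power is lost that the design has already paid for.

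Gray's test has a stratified form, but it has to be requested. An analyst following 16.d literally would run the unstratified one. If the text is instead read as open, the choice between two defensible p-values would be made after the data are seen. At stake is a missed or weakened signal on how fast eltrombopag acts, in an analysis whose purpose is to generate such signals.

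**Working it through.** **Plan's own figure.** The plan states no level or power for Gray's test. Its only power figure, 81.4% in section 16.f, belongs to the primary endpoint. With 98 vs 49 patients, 75% vs 50%, the Table 16A boundaries and a continuity-corrected pooled variance, a three-look calculation gives 80.8%, within one point. That says nothing about Gray's test, so the effect here was simulated.

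**Inputs from the documents.** Six strata of 27 (6 × 27 = 162); 2:1 allocation in blocks of 3, so 27/3 = 9 blocks and 18:9 per full stratum; platelet visits at 72 hours and weeks 1, 2, 3, 4, 6, 8, 10 and 12.

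**Assumptions not in the documents.**
- Control week-12 incidence p differs by stratum, as listed in the table.
- Subdistribution hazard ratio 1 (null), 1.7 or 2.0.
- 9% of patients have a competing event and never respond. The figure is borrowed from the plan's non-informative share, since 16.d does not say which events compete.
- Horizon of 12 weeks, all strata full, no random censoring.

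**Data generation.** Control cumulative hazard at week 12 is H = −ln(1 − p), multiplied by the hazard ratio on eltrombopag. At p = 0.50 and a ratio of 2.0, eltrombopag incidence is 1 − 0.50² = 0.75 before the 9% dilution. Response is recorded at the next scheduled visit.

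**Test.** With no random censoring, Gray's test (ρ = 0) is close to a log-rank test in which patients with a competing event stay at risk:

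Z = Σ(d₁ − d·n₁/n) / √Σ[d·(n₁/n)(1 − n₁/n)(n − d)/(n − 1)]

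Here d and n are responses and patients at risk at a visit, and subscript 1 is the eltrombopag arm. The unstratified test sums over visits in the pooled cohort. The stratified test sums over visits within each of the six strata.

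**Results** (40,000 trials per setting; unstratified vs stratified; two-sided nominal 0.05):

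| Control week-12 incidence across strata | Size | Power, HR 1.7 | Power, HR 2.0 | Gain from stratifying at HR 2.0 |
|---|---|---|---|---|
| 50% in all | 0.051 vs 0.051 | 0.585 vs 0.579 | 0.818 vs 0.813 | −0.5 point |
| 40-60% | 0.049 vs 0.050 | 0.562 vs 0.567 | 0.807 vs 0.809 | +0.2 |
| 30-70% | 0.044 vs 0.051 | 0.521 vs 0.555 | 0.772 vs 0.798 | +2.6 |
| Treatment status only, 35/65% | 0.042 vs 0.051 | 0.505 vs 0.548 | 0.760 vs 0.794 | +3.4 |
| 15-85% | 0.028 vs 0.050 | 0.390 vs 0.512 | 0.630 vs 0.750 | +12.0 |

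Monte Carlo error on a size of 0.05 is 1.96 × √(0.05 × 0.95/40,000) ≈ 0.002.

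**Cross-check of the mechanism.** If an over-large variance is the whole explanation, size should equal 2[1 − Φ(1.96/√v)], where v is the simulated null variance of the unstratified Z. For 30-70%, v = 0.947 gives 1.96/0.973 = 2.014 and size 0.044. For 35/65%, v = 0.921 gives 2.042 and 0.041. For 15-85%, v = 0.804 gives 2.186 and 0.029. These match the simulated 0.044, 0.042 and 0.028. The stratified Z has v between 1.001 and 1.014 throughout, so it holds its level.

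**The case against.** The strongest reply is that the plan is silent rather than wrong. A reader might infer that 16.d prescribes an unstratified test; it does not use that word, and a stratified Gray's test would not contradict it. The contrast with the CMH tests is also softer than it looks. CMH is stratified by construction, but section 16 does not list its strata either. This stands as a limit on the wording. It does not remove the point, because Gray's test named without strata is, by default, the unstratified one.

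Second, a reader might infer from the Background that loss of level and power is certain. The documents do not support that. The sentence concerns resolution of ITP, not speed of platelet rise on treatment. Of the two predictors it names, only age is a stratification factor; duration of symptoms is not. Nothing quantifies the prognostic value of up-front treatment status, although the factor separates untreated patients from those who have already failed management. With strata that do not matter, the unstratified test is marginally the better of the two.

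Third, no conclusion of the trial rests on this test. It has no assigned level or power to miss, its findings are declared to need independent confirmation, and any error lies on the conservative side. All of this stands, and it sets the severity.

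**Conclusion.** The point holds conditionally and is minor. If the randomisation strata predict time to response and Gray's test is run without them, the test is conservative. Under mild to moderate assumed spread, size is about 0.042 to 0.049 instead of 0.05, with about 0 to 3 points of power lost at a subdistribution hazard ratio of 2.0 (up to about 4 points at 1.7). Only an extreme 15-85% spread brings size to 0.028 and a loss of about 12 points; that is a bound, not an expectation. With non-prognostic strata nothing is gained, and stratifying costs about 0.5 point.

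These sizes rest on the assumed incidence spreads, hazard ratios, 9% competing share, 12-week horizon and full strata. Strata that fill unevenly, or an early stop, were not examined. The direction needs only that the strata are prognostic. It would be wrong to read this as a threat to the primary CMH result or as a source of false positives; neither follows.

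**What to change.** In section 16.d, directly after Gray's test is named, insert: *stratified by the randomisation strata (age group and up-front treatment status)*. The rest of the sentence can stay.

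The cost is one phrase in the plan and one argument in the software call. Data collection, sample size and trial conduct do not change. The statistical price is about half a point of power if the strata turn out not to matter. In return the test matches the design, held its level in every setting simulated, and leaves no choice of p-value to be made after the data are seen.

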9.3 HRQoL Tools

The Kids ITP tool (KIT) will be performed at Baseline/Screening, at Study Visits Week 1, Week 4, Week 12, and 1 year. The KIT is the first disease-specific health related quality of life measure developed for ITP, specifically for use with children. It contains a child self-report version (to be completed by children ages 7 and older), a parent proxy version (to be completed by parents of children age 2 and older), and parent version (to assess parental impact of ITP - all ages). Each version consists of 26 items, and a single overall score is obtained. Scores range from 0 to 100: a higher score represents better quality of life or, as with the parental impact version, less burden. Response options are on a 5-point Likert-type scale ranging from "never" to "always", and the timeframe of interest is the "past week". KIT will be administered in English, Spanish, or Quebec French.

Assessment of global change will be performed at Week 1, Week 4, Week 12, and 1 year using the Parent Proxy-Report and Child Self-Report Change Scales.

Assessment of fatigue will be performed at Baseline/Screening, at Study Visits Week 1, Week 4, Week 12, and 1 year using the Fatigue Scale-Child (FS-C to be administered by children ages 7 to 12 years), the Fatigue Scale-Adolescent (FS-A teens ages 13 and older), and the Fatigue Scale-Parent (FS-P to be completed by parents of children of all ages). Each item has a 5-point Likert-type format; total scale intensity ratings have been rescaled so that they range from 0 (no fatigue symptoms) to 100 (highest possible fatigue score). All of the tools have been evaluated for face, content, and construct validity and for internal consistency. The tools take five minutes to complete. Fatigue scales will be administered in English.

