The National Institute of Health funded and developed the web based patient-reported outcomes measurement information system (PROMIS®). PROMIS® contains a number of pediatric self-report short items that each assess domains of physical and emotional function in general and over a seven-day time interval [20-23](#). Patients (age 7-18 years) will complete PROMIS® global health pediatric measures (Appendix A2c). These measures have been tested and reliability of each is ≥ 0.85 over 2 to 4 standard deviations [23-27](#). Each of the measures consists of ten questions. Three questions ask the participant to respond based on the past 7 days. Responses utilize a 5-point Likert scale ranging from "excellent" to "poor" or "never" to "always" [21,24](#). The PROMIS®

measures will be scored in accordance with their scoring manuals ²⁴⁻²⁷. PROMIS will be administered in English and Spanish.

Patients may be excluded from participation in Patient Reported Outcome Measures (PROMIS, KIT, Change Scale, and Hockenberry Fatigue Scale) if a translated tool is not available.

HRQoL surveys may be completed remotely and emailed, mailed, or faxed to study site if associated study visit is performed remotely due to pandemic-related safety or research restrictions.

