To address secondary objective 3.2.2, an ANCOVA model will be used to compare the number of rescue therapies between the two arms.

To address secondary objective 3.2.3, the observed proportion and 95% confidence interval of platelet responders will be calculated in the subset of patients who required a rescue treatment during weeks 1-2 of the study.

To address secondary objective 3.2.4, the Cochran-Mantel-Haenszel test will be used to compare the proportion of patients who do not need ongoing treatment at 12 weeks and 6 months between the two arms.

To address secondary objective 3.2.5, the Cochran-Mantel-Haenszel test will be used to compare the proportion of patients with a treatment response at one year between the two arms.

To address secondary objective 3.2.6, an ANCOVA model will be used to compare the number of 2nd-line therapies between the two arms

To address secondary objective 3.2.7, an ANCOVA model will be used to compare the absolute change from baseline in percentage of regulatory T cells at 12 weeks and 1 year between the two arms

To address secondary objective 3.2.8, KIT scores will be calculated as per the methods described in Klaassen et al.²⁸ Spaghetti plots will be used to visualize the KIT scores over time per patient by treatment arm. An ANCOVA model will be used to compare the absolute change from baseline in KIT overall score at 1 week, 4 weeks, 12 weeks, and 1 year between the two arms. An ANCOVA model will be used to compare the Change Scale score at 1 week, 4 weeks, 12 weeks, and 1 year between the two arms.

To address secondary objective 3.2.9, fatigue scores will be calculated as per the methods described in Hockenberry et al.²⁹ All measures will be rescaled from 0 (no fatigue) to 100 (high fatigue) for consistency in scoring. Spaghetti plots will be used to visualize the fatigue scores over time per patient by treatment arm. The PROMIS tired question: “My child (I) got tired easily never to almost always” will be used as an anchor with severe fatigue defined as “often” or “almost always” with moderate fatigue being “sometimes”. An ANCOVA model will be used to compare the absolute change from baseline in fatigue at 1 week, 4 weeks, 12 weeks, and 1 year between the two arms.

To address secondary objective 3.2.10, an ANCOVA model will be used to compare iron indices at 12 weeks, 6 months, and 1 year between the two arms

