To address the survey-related aspects of exploratory objectives 3.3.3, the PROMIS® measures will be scored as according to the described approach ²². Mixed-effects model and the generalized estimating equations (GEE) allow for covariate adjustment and can model both within group effects (time) and between group effects ³⁰. The results will be summarized with adjusted means with associated 95% confidence intervals at each time point for each treatment group. For the primary analysis, these models will include the main effect of time (T0-T2). PHIS is a confidential database that allows use among the 47 member hospitals including a number of prominent pediatric hematology centers that participate in ICON. Descriptive analysis will be performed using PHIS data after patients have been identified using PHIS diagnosis codes to identify patients with ITP. Descriptive statistics will be performed to analyze financial burden measures. As instruments have not been validated, item level comparisons will be made between standard therapy and eltrombopag.

During the trial, on an ongoing basis the study team will monitor the response rate to each of the surveys. A patient will be counted as having responded to a given survey if both the baseline survey and at least one post-baseline survey are submitted. If the observed response rate for a given survey falls below 33%, the study team may consider halting the collection of that survey from subsequent patients, as it is an inappropriate use of resources, and unfair to patients, to continue to require survey submission if the survey data will be too sparse to address the study objective.

e. Interim Analysis

Interim analysis for efficacy and futility

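### The survey-halting rule in 16.d requires a baseline form, so the Global Change Scale, which has none, always shows a 0% response rate

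*Combined protocol and SAP*

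**What the plan says.** The rule closes section 16.d (Analysis of Exploratory Objectives). Throughout the trial, "the study team will monitor the response rate to each of the surveys". A patient is "counted as having responded to a given survey if both the baseline survey and at least one post-baseline survey are submitted". The consequence is stated as follows: "If the observed response rate for a given survey falls below 33%, the study team may consider halting the collection of that survey". A halt would apply to patients who come later. The reason given is that requiring surveys whose data will be too thin to be useful wastes resources and is unfair to patients. The rule names no exception and no denominator.

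Section 9.3 sets the survey schedules:
- KIT: "The Kids ITP tool (KIT) will be performed at Baseline/Screening, at Study Visits Week 1, Week 4, Week 12, and 1 year".
- Fatigue: "Assessment of fatigue will be performed at Baseline/Screening, at Study Visits Week 1, Week 4, Week 12, and 1 year".
- Change Scale: "Assessment of global change will be performed at Week 1, Week 4, Week 12, and 1 year".

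Only the third has no baseline assessment. The same section counts the Change Scale among the "Patient Reported Outcome Measures (PROMIS, KIT, Change Scale, and Hockenberry Fatigue Scale").

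The Change Scale data have a planned use. Objective 3.2.8 names the scale, and section 16.c states for that objective: "An ANCOVA model will be used to compare the Change Scale score at 1 week, 4 weeks, 12 weeks, and 1 year". The endpoint lists place it lower. Secondary endpoint 5.2.8 covers only the parent-proxy KIT score, and Change Scale scores appear under exploratory endpoint 5.3.2.

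**The concern.** One responder definition is written for all surveys, but it suits only instruments measured as change from a baseline score. The Change Scale measures change directly: the parent or child rates how quality of life has moved since the study began. A baseline version would have no meaning, and none is scheduled. The monitoring figure for this instrument is thus fixed by the wording of the rule and not by how many forms come back.

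At stake is a decision on whether to go on collecting a measure that a secondary objective names. A team following the text would see the halting condition met from the first check onward. A team that saw the artefact would have to devise its own definition while an open-label trial is running. Forms not collected from later patients cannot be recovered.

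**Working it through.** The 33% cut-off is a chosen threshold, not a calculated one, so there is no plan figure to reproduce. The check applies the rule to the schedule.

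**Inputs**
- Responder definition, scope and 33% threshold: section 16.d.
- Change Scale visits: Weeks 1, 4 and 12 and 1 year (section 9.3). Endpoint 5.3.2 gives the same four times. The schedule table in section 9 is broken in the extracted text, but what can be read agrees.
- Item wording: Appendix A2, Change Scale, both parent and child versions, asks about change from the start of the study.
- Maximum enrolment 162, with 108 and 54 per arm (section 16.f).

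**Rule as written**

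Response rate = (patients with a baseline form AND at least one post-baseline form) / n.

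For the Change Scale the number of patients with a baseline form is 0, so the numerator is 0 whatever the post-baseline return:
- 0/54 = 0%
- 0/108 = 0%
- 0/162 = 0%

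Since 0% < 33%, the condition is met at every check. The missing denominator makes no difference, because a zero numerator gives 0% for any n.

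**Comparison with a survey that has a baseline form**

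Suppose 90% return at baseline and, independently, 90% return at least one later form (assumed rates, not in the documents). The rule gives 0.90 × 0.90 = 81%, well above 33%. The same post-baseline return on the Change Scale gives 0%.

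**Rule with the baseline requirement removed for the Change Scale**

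Response rate = (patients with at least one post-baseline form) / n. This follows actual return. The binomial probability that the observed rate is at least 33%, for assumed true return rates, is:

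| True return (assumed) | n = 54 | n = 162 |
|---|---|---|
| 20% | 0.0149 | below 0.0001 |
| 50% | 0.9955 | about 1.0 |
| 90% or 100% | 1.0 | 1.0 |

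Under this definition the 33% line separates poor from adequate return. As written, the rule cannot tell them apart.

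**The case against.** **Halting is only an option.** This stands. The team may consider it, the halt would affect only later patients, and forms already received stay in the data. A rate of exactly 0% alongside returned forms would also probably be noticed. That limits the harm, but the pre-specified figure still carries no information for this survey.

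**The rule may not cover the Change Scale.** It follows directly on the text about the survey aspects of objective 3.3.3 and could be confined to those surveys. This reading is possible and lowers certainty. The wording is general, however, and section 9.3 lists the Change Scale with the other patient-reported measures. If a narrow scope is meant, the text should say so.

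**The measure ranks low.** Partly right. Change Scale scores are listed only as an exploratory endpoint, and section 16.d treats exploratory findings as needing independent confirmation. But objective 3.2.8 names the scale, and section 16.c gives it its own comparison under that objective.

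**Stronger readings that a reader might infer.** One is that the rule also fails for KIT and fatigue, because baseline plus a single early form counts as response even if later visits are empty. The documents do not make this an error. A lenient definition errs towards continued collection, so it loses no data, and any shortfall in power at late visits would come from missing forms and not from the rule. Another is that PROMIS, whose first post-baseline form is due at Week 12, would misfire early in accrual. That depends on counting patients whose form is not yet due, and the rule does not say to count them. It would also pass as accrual proceeds.

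**Conclusion.** The point holds for the Global Change Scale only, and it is minor. Under section 16.d as written, the scale's response rate is 0% at any true completion, so the condition for considering a halt is always met and does not reflect how many forms are returned. This rests on two readings: that the rule covers every survey, as its wording says, and that the Change Scale has no baseline form, as section 9.3 and the item wording show. No outside figure is needed. The return rates used for illustration are assumptions, and the 0% result does not depend on them.

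A reader might go further and infer that Change Scale collection will be stopped or that objective 3.2.8 is lost. The documents do not support this. Meeting the condition permits a discussion and does not require action, the KIT part of objective 3.2.8 has baseline forms and is monitored properly, and the primary endpoint is not involved.

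**What to change.** In section 16.d, reword the responder definition so that a baseline form is required only for surveys that have a scheduled baseline form. State that for the Change Scale a responder is a patient with at least one post-baseline form submitted. If the rule is meant only for the surveys of objective 3.3.3, say that instead.

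The 33% threshold and the discretion to halt can stay as they are. Separate triggers for each visit are not needed to repair this gap. They would also be open to debate, since a low 1-year return could then permit halting a survey that has good data up to Week 12.

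The cost is one clause in section 16.d and a matching change to the tracking report, with no new data and no extra patients.
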